8.1.5 End of Study

The End of Study visit is defined as the date of the final study visit (eg, final long-term follow-up visit) when assessments and/or procedures are performed.

8.2 General Assessments

8.2.1 Informed Consent

All subjects or their legally authorized representative must sign and personally date the IRB/IEC approved informed consent before any study-specific procedures are performed.

8.2.2 Demographics

Demographic data collection including sex, age, race, and ethnicity will be collected in order to study their possible association with subject safety and treatment effectiveness. Additionally, demographic data will be used to study the impact on biomarkers variability and PK of the protocol-required therapies.

8.2.3 Medical History

The investigator or designee will collect a complete medical and surgical history that started prior to enrollment through the time of consent. Medical history will include information on the subject's concurrent medical conditions. Record all findings on the medical history CRF. In addition to the medical history above, SCLC history must date

Protocol Number: 20200439

Date: 05 June 2024 Page 94 of 176

back to the original diagnosis. Relevant medical history, including antecedent hematologic or oncologic disease, other diseases/symptoms such as fatigue, bleeding, and infection (resolved and ongoing) will be collected. The current toxicity grade will be collected for each condition that has not resolved. Any unresolved medical history will be graded according to the CTCAE version 4.0 (See Section 11.4) unless specified otherwise.

All prior cancer therapies will be collected.

8.2.4 Physical Examination

Physical examination will be performed as per standard of care. Physical examination findings should be recorded on the appropriate CRF (eg, medical history, event).

8.2.5 Physical Measurements

Height (in centimeters) and weight (in kilograms) should be measured without shoes.

8.2.6 Substance Abuse History

Obtain a detailed history of prior and/or concurrent use of tobacco.

[figure not shown]
8.2.7 Performance Status

The subject's performance status will be assessed using the ECOG performance scale (see Section 11.8).

8.3 Efficacy Assessments

8.3.1 Radiologic Imaging Assessment

[figure not shown]
The extent of disease will be evaluated by contrast-enhanced MRI/computed tomography (CT) according to modified RECIST 1.1 (Section 11.9).

Protocol Number: 20200439

Date: 05 June 2024 Page 95 of 176

Protocol Number: 20200439

Date: 05 June 2024 Page 96 of 176

8.4 Safety Assessments

Planned time points for all safety assessments are listed in the Schedule of Activities see (Section 1.3).

8.4.1 Vital Signs and Pulse Oximetry

Vitals signs (blood pressure [BP], RR, HR, and temperature) and pulse oximetry will be recorded by the investigator or designee at time points specified in the Schedule of Assessments (Section 1.3).

The following measurements must be performed: systolic/diastolic BP, HR, RR, and temperature. Subject must be in a rested and calm state for at least 5 minutes before blood pressure assessments are conducted. The position selected for a subject should be the same that is used throughout the study and documented on the vital sign CRF. The temperature location selected for a subject should be the same **as** that used throughout the study and documented on the vital signs CRF. Record all measurements on the vital signs CRF.

In subjects with an initial blood pressure reading within the hypertensive range, a second reading should be taken at least 1 minute after the initial reading, with the 2 readings averaged to obtain a final blood pressure measurement. The average value should be recorded in the eCRF.

Oxygen saturation will be measured using a standard pulse oximeter. The subject must be in a rested and calm state for at least 5 minutes before pulse oximetry assessments are completed.

Vital signs will be taken pre-AMG 404 infusion and at AMG 404 EOI. After each tarlatamab infusion for the first 2 cycles (during the hospitalization period), vital signs will be assessed accordingly during the following timepoints:

Protocol Number: 20200439

Date: 05 June 2024 Page 97 of 176

8.4.2 Neurological Examination

A neurological examination will be performed as outlined in the Schedule of Activities (Section 1.3). Subjects will be specifically queried for neurological symptoms observed in the interval since the last extended neurological examination. Abnormalities of the following should be recorded: level of consciousness, orientation, vision, cranial nerves and brain stem functions, pyramidal and extra pyramidal motor system, reflexes, muscle tone and trophic findings, coordination, sensory system, neuropsychological findings (eg, speech, cognition, and emotion).

The individual performing the neurological examination will characterize the findings as either normal or abnormal. Abnormal findings found predose will be reported on the medical history page of the eCRF. Abnormal findings found after the subject is dosed will be reported on the Event page of the eCRF.

A more detailed neurological assessment may be performed in subjects at selected sites.

8.4.3 Writing Test

Subjects will be asked to provide writing tests in order to detect early cerebellar signs as outlined in the Schedule of Activities (Section 1.3). Subjects will write down the current date, location of the clinic, and the current time in a sentence. The sentence format should be repeated each time throughout the study. Interpretation of writing sample results will be based solely on the investigator's assessment.

8.4.4 Mini-Mental Status Examination

The Mini Mental Status Examination (MMSE) Version 2 will be performed as outlined in the Schedule of Activities (Section 1.3). The MMSE is a 30-point healthcare professional (including study coordinators) administered questionnaire to assess potential subjects for cognitive impairment. The assessment covers 8 categories, such as orientation to time, orientation to place or language, with a total score that ranges from 0 to 30 (30 indicates the best possible outcome). The overall total score should be recorded on the appropriate eCRFs.

8.4.5 Electrocardiograms (ECGs)

Subject must be in supine position in a rested and calm state for at least 5 minutes before ECG assessment is conducted. If the subject is unable to be in the supine position, the subject should be in most recumbent position as possible. The ECG must include the following measurements: Heart Rate, QRS, QT, QTc, and PR intervals. The

Protocol Number: 20200439

Date: 05 June 2024 Page 98 of 176

Principal Investigator will review all ECGs. Once signed, the original ECG tracing will be retained with the subject's source documents. At the request of the sponsor, a copy of the original ECG will be made available to Amgen. See Section 1.3 for timing of ECG assessments.

8.4.6 Clinical Laboratory Assessments

Refer to Section 11.2 for the list of clinical laboratory tests to be performed and to the Schedule of Activities (Section 1.3) for the timing and frequency.

The investigator is responsible for reviewing laboratory test results and recording any clinically relevant changes occurring during the study in the Event CRF. The investigator must determine whether an abnormal value in an individual study subject represents a clinically significant change from the subject's baseline values. In general, abnormal laboratory findings without clinical significance (based on the investigator's judgment) are not to be recorded as adverse events. However, laboratory value changes that require treatment or adjustment in current therapy are considered adverse events. Where applicable, clinical sequelae (not the laboratory abnormality) are to be recorded as the adverse event.

All protocol-required laboratory assessments, as defined in Section 11.2, must be conducted in accordance with the laboratory manual and the Schedule of Activities (Section 1.3).

8.4.7 Vital Status

Vital status must be obtained for all subjects within the limits of local law. This includes subjects who may have discontinued study visits with or without withdrawing consent and should include interrogation of public databases, if necessary. If deceased, the date and reported cause of death should be obtained.

8.4.8 Other Safety

8.4.8.1 Echocardiogram (ECHO)/Multigated Acquisition (MUGA) Scan

Echocardiogram or MUGA will be performed to assess cardiac ejection fraction and will occur at time points specified in the Schedule of Activities (Section 1.3).

Echocardiography/MUGA should include an evaluation from left ventricular ejection fraction (LVEF). Additional ECHO/MUGA assessments may be performed as clinically indicated. For subjects developing COVID-19 during screening period and following screening imaging assessments, consider repeating ECHO following resolution.

Protocol Number: 20200439

Date: 05 June 2024 Page 99 of 176

8.4.8.2 Hypersensitivity

Hypersensitivity reactions have been reported in patients treated with tarlatamab including rare severe events. Clinical signs and symptoms of hypersensitivity may include but are not limited to rash and bronchospasm. Monitor patients for signs and symptoms of hypersensitivity during treatment with tarlatamab and manage as clinically indicated. Withhold or consider permanent discontinuation of tarlatamab based on severity.

- 8.4.9 Adverse Events and Serious Adverse Events
- 8.4.9.1 Time Period and Frequency for Collecting and Reporting Safety Event Information

8.4.9.1.1 Adverse Events

The adverse event grading scale to be used for this study will be the CTCAE and is described in Section 11.4.

The investigator is responsible for ensuring that all adverse events observed by the investigator or reported by the subject that occur after the first dose of investigational products through the second safety follow-up visit or 60 days after the last dose of investigational product(s), whichever is later, are reported using the Events CRF.

8.4.9.1.2 Serious Adverse Events

The investigator is responsible for ensuring that all serious adverse events observed by the investigator or reported by the subject that occur after signing of the informed consent through the second safety follow-up visit or 60 days after the last dose of investigational product(s), whichever is later, are reported using the Events CRF.

All serious adverse events will be collected, recorded, and reported to the sponsor or designee immediately and no later than 24 hours of the investigator's awareness of the event, as indicated in Section 11.4. The investigator will submit any updated serious adverse event data to the sponsor immediately and no later than 24 hours of it being available.

The criteria for grade 4 in the CTCAE grading scale differs from the regulatory criteria for serious adverse events. It is left to the investigator's judgment to also report these grade 4 abnormalities as serious adverse events. For any adverse event that applies to this situation, comprehensive documentation of the event's severity must be recorded in the subject medical records.

Protocol Number: 20200439

Date: 05 June 2024 Page 100 of 176

8.4.9.1.3 Reporting Serious Adverse Events After the Protocol-required Reporting Period

During the long-term follow-up period, if the investigator becomes aware of serious adverse events suspected to be related to investigational product and all fatal serious adverse events (regardless of causality), then these serious adverse events will be reported to Amgen. The investigator will report serious adverse events to Amgen immediately and no later than 24 hours after the investigator's awareness of the event on the Events CRF.

There is no requirement to actively monitor study subjects after the study has ended with regards to study subjects treated by the investigator. However, if the investigator becomes aware of serious adverse events suspected to be related to investigational product after the study has ended, then these serious adverse events will be reported to Amgen immediately and no later than 24 hours after the investigator's awareness of the event.

Serious adverse events reported after the end of study will be captured within the safety database as clinical trial cases and handled accordingly based on relationship to investigational product.

If further safety related data is needed to fulfill any regulatory reporting requirements for a reportable event, then additional information may need to be collected from the subject's records if the subject ends the study.

The method of recording, evaluating, and assessing causality of adverse events, and serious adverse events and the procedures for completing and transmitting serious adverse event reports are provided in Section 11.4.

8.4.9.2 Method of Detecting Adverse Events and Serious Adverse Events

Care will be taken not to introduce bias when detecting adverse events and/or serious adverse events. Open-ended and non-leading verbal questioning of the subject is the preferred method to inquire about adverse event occurrence.

8.4.9.3 Follow-up of Adverse Events and Serious Adverse Events

After the initial adverse event/serious adverse event report, the investigator is required to proactively follow each subject at subsequent visits/contacts. All adverse events and serious adverse events will be followed until resolution, stabilization, until the event is otherwise explained, or the subject is lost to follow-up (as defined in Section 7.4). Further information on follow-up procedures is given in Section 11.4.

Protocol Number: 20200439

Date: 05 June 2024 Page 101 of 176

All new information for previously reported serious adverse events must be sent to Amgen immediately and no later than 24 hours following awareness of the new information. If specifically requested, the investigator may need to provide additional follow-up information, such as discharge summaries, medical records, or extracts from the medical records. Information provided about the serious adverse event must be consistent with that recorded on the Events CRF.

8.4.9.4 Regulatory Reporting Requirements for Serious Adverse Events If subject is permanently withdrawn from protocol-required therapies because of a serious adverse event, this information must be submitted to Amgen.

Prompt notification by the investigator to the sponsor of serious adverse events is essential so that legal obligations and ethical responsibilities towards the safety of subjects and the safety of a study treatment under clinical investigation are met.

The sponsor has a legal responsibility to notify both the local regulatory authority and other regulatory agencies about the safety of a study treatment under clinical investigation. The sponsor will comply with country-specific regulatory requirements relating to safety reporting to the regulatory authority, IRBs/IECs, and investigators.

Individual safety reports must be prepared for suspected unexpected serious adverse reactions according to local regulatory requirements and sponsor policy and forwarded to investigators as necessary.

An investigator who receives an individual safety report describing a serious adverse event or other specific safety information (eg, summary or listing of serious adverse events) from the sponsor, will file it along with the Investigator's Brochure and will notify the IRB/IEC, if appropriate according to local requirements.

Amgen will prepare a single Development Safety Update Report (DSUR) (also referred to as Annual Safety Report [ASR] in the European Union) for the Amgen Investigational Product. In order to ensure that consolidated safety information for the trial is provided, this single DSUR will also include appropriate information on any other investigational products used in the clinical trial, if applicable.

8.4.9.5 Safety Monitoring Plan

Subject safety will be routinely monitored as defined in Amgen's safety surveillance and signal management processes.

Protocol Number: 20200439

Date: 05 June 2024 Page 102 of 176

8.4.9.6 Pregnancy and Lactation

Details of all pregnancies and/or lactation in female subjects and female partners of male subjects will be collected after the start of study treatment and until days, after the last dose of tarlatamab and days for female study subjects and days for female partners of male study subjects after the last dose of AMG 404.

If a pregnancy is reported, the investigator is to inform Amgen immediately and no later than 24 hours of learning of the pregnancy and/or lactation and is to follow the procedures outlined in Section 11.5. Amgen Global Patient Safety will follow-up with the investigator regarding additional information that may be requested.

Abnormal pregnancy outcomes (eg, spontaneous abortion, fetal death, stillbirth, congenital anomalies, ectopic pregnancy) are considered serious adverse events.

Further details regarding pregnancy and lactation are provided in Section 11.5.

Pregnancy Testing

A highly sensitive (urine or serum) pregnancy test should be completed at screening and within days of initiation of investigational product for females of childbearing potential.

Note: Females who have undergone a bilateral tubal ligation/occlusion should have pregnancy testing per protocol requirements. If a female subject, or the partner of a male subject, becomes pregnant it must be reported on the Pregnancy Notification Form, see Figure 11-2. Refer to Section 11.5 for contraceptive requirements.

A pregnancy test should be performed after the last dose of tarlatamab and days after the last dose of AMG 404.

Additional on-treatment pregnancy testing may be performed at the investigator's discretion or as required per local laws and regulations.

8.5 Pharmacokinetic Assessments

All subjects enrolled in the study will have PK samples assessed.

Blood samples will be collected for measurement of serum concentrations of tarlatamab, and AMG 404 as specified in the Schedule of Activities (Section 1.3). Instructions for the collection and handling of biological samples will be provided by the sponsor. The actual date and time (24-hour clock time) of each sample will be recorded.

[figure not shown]

Product: Tarlatamab (AMG 757), AMG 404 Protocol Number: 20200439 Date: 05 June 2024

Page 103 of 176

Product: Tarlatamab (AMG 757), AMG 404 **Protocol Number:** 20200439

[figure not shown]
Date: 05 June 2024 Page 104 of 176

Protocol Number: 20200439

Date: 05 June 2024

9. Statistical Considerations

9.1 Statistical Hypotheses

No formal statistical hypothesis will be tested.

9.2 Sample Size Determination

Approximately subjects were anticipated to be enrolled in the study (up to subjects in a dose exploration phase, and the remaining subjects enrolled in a dose expansion phase). Study enrollment ended in subjects in Part 1, and subjects in Part 2.

Dose Exploration Phase:

Up to 6 planned dose cohorts will be examined during dose exploration. The planned dose levels for tarlatamab with a fixed dose of AMG 404 (mg IV mg IV are described in Section 4.1.

Dose exploration will begin with subjects treated at Dose Cohort Level 1. The study DLT period is days. Once all subjects enrolled at a certain Dose Cohort Level are DLT evaluable, a DLRT meeting will be convened. Depending on observed safety data, the following may occur: 1) dose de-escalation to the next lowest Dose Cohort Level, 2) additional enrollment to the current Dose Cohort Level, or 3) dose escalation to the next highest Dose Cohort Level or initiation of enrollment in Part 2. In order to consider a certain Dose Level as the recommended phase 2 dose, at least

DLT-evaluable subjects must be enrolled at that Dose Level.

Protocol Number: 20200439

Date: 05 June 2024 Page 106 of 176

These sample sizes are based on practical considerations and are consistent with conventional oncology studies with the objective to estimate the recommended phase 2 dose and to evaluate initial safety and tolerability. The probability of observing at least 1 DLT if the true DLT rate is 10 to 30% is provided in Table 9-1 for various number of subjects.

 Number of Subjects
 10% DLT Rate
 30% DLT Rate

 19
 55

 27
 70

 34
 80

 47
 91

 57
 96

65

Table 9-1. Probability of Observing at Least 1 DLT

DLT = dose-limiting toxicity

Dose Expansion Phase:

If the sample size in the dose expansion phase of 10 (or 20). There is 65% (88%) probability of observing at least 1 adverse event with 10% incidence rate, and the 95% exact confidence interval for 20% objective response (OR) is 3% to 56% (6% to 44%).

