9.4.2.5 Adaptive Design

The guidelines described in Section 4.1 for dose escalation or de-escalation to the next dose level are determined by using a mTPI-2 algorithm (Guo et al, 2017) with one practical modification. Consistent with conventional oncology phase 1 study designs (eg, 3+3 design) and given the imprecision with making decisions using as few as subjects, in the instance of 1 DLT in the initial subjects at a dose level then, as appropriate, the design allows expansion at the dose level beyond subjects. All other dose escalation or de-escalation rules are determined strictly by the mTPI-2 algorithm as described below. The mTPI-2 algorithm employs a simple beta-binomial Bayesian model. Let p_T be the target toxicity level and $(p_T - \epsilon_1, p_T + \epsilon_2)$ be the equivalence toxicity interval denoted as EI. The unit toxicity interval (0, 1) is divided into subintervals with equal length given by $(\epsilon_1 + \epsilon_2)$. Let the under-dosing intervals (LI) denote for a set of intervals below EI, and the overdosing intervals (HI) for a set of intervals above EI. The 3 types of dosing intervals (EI, LI, HI) are associated with 3 different dose-escalation

Protocol Number: 20200439

Date: 05 June 2024 Page 113 of 176

decisions. The LI correspond to a dose escalation (E), the HI corresponds to a dose de-escalation (D), and proper dosing intervals (EI) correspond to staying at the current dose (S). This study design uses a target toxicity level, p_T of 30%, and EI of (25%, 33%).

Decision rules are based on the unit probability mass (UPM) calculated on these equal-length intervals. Given an interval and a probability distribution, the UPM of that interval is defined as the probability of the interval divided by the length of the interval. The mTPI-2 design calculates the UPMs for each of equal-length dosing intervals. If the interval with the largest UPM is from LI, EI, or HI, then the corresponding dose decision would be E, S, or D, respectively.

A dose level will be considered unsafe, with no additional subjects enrolled at that dose level, if it has an estimated 95% or more probability of exceeding the target DLT rate p_T (ie, P [DLT > p_T | data] > 95%). Based on this rule, the following instances would result in a dose level being considered unsafe.

- or more DLTs in ≤ subjects
- or more DLTs in ≤ subjects
- or more DLTs in ≤ subjects
- or more DLTs in subjects

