3.2 Sample Size

Approximately subjects were anticipated to be enrolled in the study (up to subjects in a dose exploration phase, and the remaining subjects enrolled in a dose expansion phase).

Date: 27 Sep 2024 Page 18 of 51

Study enrollment ended in subjects. A total of subjects were enrolled in this study including subjects in Part 1, and subjects in Part 2.

Dose Exploration Phase:

Up to 6 planned dose cohorts will be examined during dose exploration. The planned dose levels for tarlatamab with a fixed dose of AMG 404 (mg IV are described in protocol section 4.1.

These sample sizes are based on practical considerations and are consistent with conventional oncology studies with the objective to estimate the recommended phase 2 target dose and to evaluate initial safety and tolerability. The probability of observing at least 1 DLT if the true DLT rate is 10 to 30% is provided in Table 3 for various number of subjects.

Table 3. Probability of Observing at least 1 DLT

Number of Subjects	10% DLT Rate	30% DLT Rate
	19	55
	27	70
	34	80
	47	91
	57	96
	65	98

DLT = dose-limiting toxicity

Dose Expansion Phase:

Date: 27 Sep 2024 Page 19 of 51

If the sample size in the dose expansion phase of There is 65% (88%) probability of observing at least 1 adverse event with 10% incidence rate, and the 95% exact confidence interval for 20% objective response (OR) is 3% to 56% (6% to 44%).

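### The 30% column of the DLT-detection table holds values for a rate of about 33%, so all six probabilities are too high

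*Protocol*

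**What the plan says.** Protocol section 9.2, on the dose-exploration phase, states: "The probability of observing at least 1 DLT if the true DLT rate is 10 to 30% is provided in Table 9-1". SAP section 3.2 makes the same statement: "The probability of observing at least 1 DLT if the true DLT rate is 10 to 30% is provided in Table 3". Each table has one row per cohort size, with one column for a 10% DLT rate and one for a 30% DLT rate.

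- 10% column: 19, 27, 34, 47, 57, 65
- 30% column: 55, 70, 80, 91, 96, 98

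The cohort sizes themselves are blacked out. In the protocol text available to me the final 98 is detached from its row; the SAP prints it in place, so the last row is 65 and 98.

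Two other statements matter here. The dose-expansion paragraph of Protocol 9.2 says that 10 subjects give a 65% chance of at least one event with 10% incidence. Protocol sections 4.1 and 9.4.2.5 set the mTPI-2 target toxicity rate at 30%, with an equivalence interval of 25% to 33%.

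**The concern.** The two columns should differ only in the assumed DLT rate, because both tabulate 1 − (1 − p)^n for the same n. The 10% column behaves as expected, but the second column does not follow from a rate of 30% at the same cohort sizes. Its values are all too high, which is the favourable direction.

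The 30% rate is the target that the escalation design is built around. The table is also the only probability statement offered alongside the dose-exploration cohort sizes. A reader who uses it to judge how likely a small cohort is to reveal toxicity at the target rate is given too optimistic a figure. The same column stands in the SAP of 27 September 2024, so it could pass into the study report.

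**Working it through.** **Formula.** P(at least 1 DLT) = 1 − (1 − p)^n, where p is the true DLT rate and n the number of evaluable subjects.

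**Step 1: recover n from the 10% column.** Each printed value was matched to every integer n from 1 to 60 at p = 0.10, and each fits exactly one.

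| Printed (10%) | n | 1 − 0.90^n |
|---|---|---|
| 19 | 2 | 19.0 |
| 27 | 3 | 27.1 |
| 34 | 4 | 34.4 |
| 47 | 6 | 46.9 |
| 57 | 8 | 57.0 |
| 65 | 10 | 65.1 |

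The plan's own 10% column is therefore reproduced in full. The last row has a second anchor: the dose-expansion paragraph pairs 10 subjects with 65% at 10% incidence. The 47 and 57 arise only by rounding, not by truncation, so the table rounds.

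**Step 2: compute the second column at the labelled rate and at nearby rates.**

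| n | Printed | p = 0.30 | p = 0.33 | p = 1/3 | Printed minus value at 0.30 |
|---|---|---|---|---|---|
| 2 | 55 | 51.0 | 55.1 | 55.6 | 4.0 |
| 3 | 70 | 65.7 | 69.9 | 70.4 | 4.3 |
| 4 | 80 | 76.0 | 79.8 | 80.2 | 4.0 |
| 6 | 91 | 88.2 | 91.0 | 91.2 | 2.8 |
| 8 | 96 | 94.2 | 95.9 | 96.1 | 1.8 |
| 10 | 98 | 97.2 | 98.2 | 98.3 | 0.8 |

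At p = 0.30 no row matches after rounding (51, 66, 76, 88, 94, 97). At p = 0.33 all six do. At p = 1/3 the first row fails, because 55.6 rounds to 56. A grid search found that only rates from about 0.327 to 0.333 reproduce the whole column.

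**Step 3: check that the result does not depend on the inferred n.** At p = 0.30 the sequence for n = 1 to 5 is 30.0, 51.0, 65.7, 76.0, 83.2. It skips 55, 70 and 80 altogether, whether values are rounded or truncated. No choice of hidden cohort sizes makes this a 30% column.

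**Step 4: express the gap as the chance of missing toxicity.** The probability of no DLT is 0.70^n at a true 30% rate; the printed column corresponds to 0.67^n.

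| n | 0.70^n | 0.67^n | Ratio |
|---|---|---|---|
| 3 | 34.3% | 30.1% | 1.14 |
| 4 | 24.0% | 20.2% | 1.19 |
| 6 | 11.8% | 9.0% | 1.30 |

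**The case against.** The arithmetic is not in dispute; the objections concern consequence.

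- The documents do not rest the cohort sizes on this table. Protocol 9.2 and SAP 3.2 say the sizes were chosen on practical grounds and in line with custom in oncology trials, and the synopsis calls them empirical. No minimum detection probability is set, so no criterion fails when the column is corrected.
- Escalation, de-escalation and the unsafe-dose rule come from the mTPI-2 algorithm, with one stated practical modification. The recommended dose comes from isotonic regression. Neither uses the table.
- Enrollment ended in January 2023 (Protocol 4.1), so no cohort size can change.
- The gap is small in absolute terms. The row for n = 2 has little bearing, because Protocol 6.2.1.2 allows no escalation recommendation before three subjects are DLT-evaluable.
- The documents nowhere say that 33% was used.

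The first four points stand, and they limit the consequence to the accuracy of the record. The last stands as a caution: 33% is an inference from a six-for-six match, and its source may or may not be the upper end of the equivalence interval. None of this makes the printed figures correct for the rate in the column heading, and nothing elsewhere in either document corrects them.

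**Conclusion.** The point holds. The column labelled 30% in Protocol Table 9-1 and SAP Table 3 does not give probabilities at 30%. Every entry is too high, by about 4 points at n = 2, 3 and 4, 2.8 at n = 6, 1.8 at n = 8 and 0.8 at n = 10.

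The row-by-row comparison assumes n = 2, 3, 4, 6, 8 and 10, inferred from the 10% column because the sizes are blacked out. The finding that the label is wrong does not need that assumption, since 55, 70 and 80 cannot arise at 30% for any n. That the intended rate was 33% is likely but not stated. The error should be corrected, although it alters no dosing decision, analysis set or planned analysis.

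**What to change.** Make one of two changes, and make the same one in Protocol Table 9-1 and SAP Table 3:

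1. Keep the 30% label and replace the column with 51, 66, 76, 88, 94, 97.
2. Keep the printed values, relabel the column 33% DLT Rate, and change the introducing sentence in both sections to 10 to 33%.

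The first is preferable, because 30% is the rate the design targets. The cost is six numbers in each table, or one label and one sentence in each document under the second option. With the first, the stated detection probabilities become slightly less favourable. If the protocol will not be amended again, correct the SAP and note the discrepancy there, so that the uncorrected column is not carried into the study report.
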